9 STATISTICAL CONSIDERATIONS

9.1 DESIGN

This is a single-arm, single-center prospective study. The complete response rate will be estimated from forty enrolled subjects. An associated 95% two-sided confidence interval will be calculated using exact binomial methods. We anticipate a CR rate of 20%, which would result in a 95% two-sided confidence interval with a width of 26.6% (from 9.1% to 35.6%) for a sample size of 40 subjects. The maximum possible width of a 95% confidence interval using 40 subjects would be 32.4%.

9.2 PATIENT DISPOSITION

The disposition of patients includes the number and percentage of patients for the following categories: patients enrolled, patients treated (safety population), patients in the intent to treat population, and patients discontinued from the study. The reasons for study discontinuation will also be summarized in this table. Only one primary reason for study discontinuation will be reported in the summary. However, all reasons will be presented in the listing. A listing will present data concerning patient disposition.

9.3 PATIENT DEMOGRAPHICS AND BASELINE CHARACTERISTICS

Baseline demographic and clinical characteristics will be summarized as percentages for categorical variables and as mean, standard deviation, median, minimum and maximum for continuous measures.

9.4 EXTENT OF EXPOSURE

The dose (mg) of study drugs administered, the total number of doses of study drugs, and the duration of treatment (number of study cycles) will be summarized with descriptive statistics. The number and percentage of patients whose dose is modified at any time will be summarized by each type of modification by cycle and overall. The proportion of patients completing each cycle of treatment will be summarized.

9.5 EFFICACY ANALYSES

All patients included in the study should have a baseline tumor assessment within 60 days prior to Cycle 1/Day 1. Each patient will be assigned one of the following categories: 1) complete response or complete response with incomplete marrow recovery, 2) partial response or partial response with lymphocytosis, 3) stable disease, 4) progressive disease, 5) unknown (not assessable, insufficient data).

9.6 STATISTICAL ANALYSES

The treated population is defined as all enrolled subjects who received at least 1 dose of study drug. Efficacy and safety analysis will be based on this population.

The CR rate is defined as the proportion of patients with a best overall response of complete response with or without marrow recovery. Patients who do not have a tumor response assessment for any

reason will be considered non-responders and will be included in the denominator when calculating the CR rate.

The ORR is defined as the proportion of patients with a best overall response of partial response (PR) or complete response (CR). Patients who do not have a tumor response assessment for any reason will be considered non-responders and will be included in the denominator when calculating the ORR.

Progression-free survival is defined as the time from treatment initiation until the date of first documentation of definitive disease progression or date of death from any cause, whichever occurs first. Patients who die without a reported prior progression will be considered to have progressed on the day of their death. Patients who did not progress or are lost to follow-up will be censored at the day of their last tumor response assessment. The use of a new anticancer therapy prior to the occurrence of PD will result in censoring at the date of last tumor response assessment prior to initiation of new therapy.

The safety population includes all subjects who received at least 1 dose of study treatment. Safety evaluations will be based on the incidence, intensity, and type of adverse events, as well as on clinically significant changes in the patient's physical examination, vital signs, and clinical laboratory results. Safety variables will be tabulated and presented by study drug actually received.

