Efficacy Endpoints	The primary objective of the study is to determine the efficacy of acalabrutinib and subcutaneous rituximab as defined by complete response rate at 1 year of therapy. The complete response rate will be presented with an associated 95% two-sided exact binomial confidence interval.
Study Design	Single center, open label, Phase II trial of acalabrutinib and high frequency low dose subcutaneous rituximab in previously untreated CLL patients requiring therapy.

Premedication	
Pre-medicate patients approximately 30 minutes prior to the first dose of rituximab (administered IV) and second dose of rituximab (administered subcutaneously) with acetaminophen 650 mg (or equivalent), an antihistamine (diphenhydramine 50 mg or equivalent). Premedications will be optional prior to subsequent subcutaneous doses. Use of anti-pneumocystis (PJP) and antiviral prophylaxis is optional.

Dosing Regimen & Treatment Study Visits	
All cycles will be 28 days.
 
Rituximab: administered 2 times weekly for 6 cycles. Initial dose day 1: 50 mg IV, Then 50 mg SQ thereafter.
 
Acalabrutinib: 100 mg po BID starting on day 8 of cycle 1. First dose prior to rituximab on day 8.
 
 Response assessments will be performed prior to the completion of cycle 12. Patients who have attained a radiographic complete response will undergo a BM biopsy to confirm CR. Patients in CR will also have MRD testing performed on peripheral blood and marrow. Patients in CR and undetectable for MRD, will stop therapy and be followed until disease progression. Patients not in a MRD negative CR, will continue acalabrutinib. Repeat response assessments will be performed at 24 cycles of therapy for those continuing on acalabrutinib. Patients in CR and undetectable for MRD, will stop therapy and be followed until disease progression, unacceptable toxicity or physician/patient discretion. 
SCHEMA
 <pre> graph LR A["Acalabrutinib BID Rituximab[‡] x 6 cycles"] --> B["Acalabrutinib BID x 6 cycles"] B --> C["CR & MRD- follow off therapy"] B --> D["No CR or MRD+ Acalabrutinib"] D --> E["CT BM biopsy* MRD* (12 cycles)"] D --> F["CT BM biopsy* MRD* (24 cycles)"] E --> B F --> B </pre> 
*If otherwise in CR ‡ Administered twice weekly, 1st dose of rituximab will be administered intravenously, subsequently doses will be administered subcutaneously

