1.6 HYPOTHESIS

Combined BTK inhibitor and anti-CD20 mAb therapy has been shown to be safe and effective for treatment of CLL. [36] The rationale for use of this combination is the disparate mechanisms of actions and assumed differences in tumor cell resistance to cytotoxicity of these drugs. In addition, initiation of therapy with BTK inhibitors frequently causes lymphocytosis by mobilizing CLL cells from lymphoid tissue into the circulation where they are more susceptible to mAb mediated cytotoxicity. We propose that the combination of a BTK inhibitor and kinetically optimized high frequency low dose rituximab therapy will increase the efficacy of therapy for CLL by decreasing the time of achievement of complete response and allowing for shorter and less toxic therapy.

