4 STUDY DESIGN

4.1 OVERVIEW OF STUDY DESIGN

This is an open label, Phase II trial of acalabrutinib and high frequency low dose subcutaneous rituximab in previously untreated CLL patients requiring therapy. Subjects will be recruited from the James P. Wilmot Cancer Center, University of Rochester in Rochester, New York. Patients seen in the inpatient or outpatient setting with histologically confirmed untreated CLL will be evaluated for this study.

Patients will be treated with the following combination:

Rituximab: day 1 = 50 mg IV, then 50 mg SQ 2 x weekly for 6 cycles. Note that in the event of a first dose infusion reaction, subsequent doses may be given IV if felt necessary by the treating investigator.

Acalabrutinib: 100 mg po BID starting on day 8 of cycle 1. First dose prior to rituximab on day 8.

- Response assessments will be performed prior to the completion of cycle 12. Patients who have attained a radiographic complete response will undergo a BM biopsy to confirm CR. Patients in CR will also have MRD testing performed on peripheral blood and marrow. Patients in CR and undetectable for MRD, will stop therapy and be followed until disease progression.
- Patients not in a MRD negative CR, will continue acalabrutinib.
- Repeat response assessments will be performed at 24 cycles of therapy for those continuing on acalabrutinib. Patients in CR and undetectable for MRD, will stop therapy and be followed until disease progression, unacceptable toxicity or physician/patient discretion.

All cycles will be 28 days.

Patients will be followed until the occurrence of definitive disease progression and may discontinue therapy early for unacceptable toxicity or withdrawal from the study due to investigator decision or other reasons.

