⁶ Baseline CT scan within 60 days prior to Cycle 1/Day 1. CT Scan/Response Assessment +/- 7 day window. CT Scan/Response assessment end of cycle 12 and at the end of cycle 24 for patients continuing on acalabrutinib. Follow up CTs to be done at investigator discretion/ per standard of care. CTs at cycle 12 and 24 will not be required if a patient does not have measurable disease at baseline.

⁷ Visits every 3 months (+/- 1 month) or as per investigator discretion. Treatment Administration and labs or other assessments +/- 7 day window from visit.

⁸ Serum or urine pregnancy test prior to Cycle 1 / Day 1 and within 30 days following discontinuation for females of childbearing potential. If patient has experienced menopause or no longer has uterus / ovaries this can be omitted.

⁹ Bone Marrow sample performed prior to completion of cycle 12 and/or cycle 24 to confirm a complete response / MRD negativity

¹⁰ Flow cytometry of peripheral blood for minimal residual disease assessment is being performed prior to completion of cycle 12 and at cycle 24 for patients continuing on acalabrutinib. A patient in CR will undergo a bone marrow biopsy to confirm the response. Bone marrow and peripheral blood samples will be analyzed and stored in the laboratory of [name] at the University of Rochester.

¹¹ Follow-up for SAEs should continue until resolution, stabilization, the subject has withdrawn consent or has been lost to follow-up.

¹² Patients not in a MRD negative complete remission will continue acalabrutinib.

¹³ Acalabrutinib is dosed twice daily every day, unless treatment is held or discontinued, starting Cycle 1 Day 8.

¹⁴ At a minimum, hematology includes white blood cells and differential, hemoglobin, hematocrit, mean corpuscular volume, platelets.

¹⁵ At a minimum, chemistry includes sodium, potassium, chloride, bicarbonate, urea nitrogen, creatinine, glucose, calcium, phosphorus, albumin

¹⁶ Chemistry, uric acid and LDH will be repeated 6-8 hours after treatment initiation and as further clinically indicated for patients with a high tumor burden, which is defined as having any lymph nodes >10cm or lymph nodes >5cm with an absolute lymphocyte count>25 x10⁹/L

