8.3 DEFINITIONS OF TUMOR RESPONSE AND PROGRESSION

Responses will be categorized by the IRC as CR, CRI, PR, PR-L, SD, or PD. In addition, a response category of not evaluable (NE) is provided for situations in which there is inadequate information to otherwise categorize response status.

The best overall response will be determined. The best overall response is the best response recorded from the start of treatment until disease/recurrence progression (taking as a reference for disease progression the smallest measurements recorded since treatment started). Where imaging data are available, these data will supersede physical examination data in determining tumor status.

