8.8 NON-EVALUABLE

In a patient who does not have evidence of PD, the occurrence of any of the following conditions indicates a response status of NE:

- There are no images or inadequate or missing images
- Images of the liver and spleen are missing at that time point (with the exception that absence of splenic images will not result in an NE designation in a patient known to have undergone splenectomy).

Note: A time-point will be considered to have a response of NE if any target lesion is missing. PD may be assigned at any time point regardless of the extent of missing target or non-target lesions. Missing non-target lesions will not impact the ability to assess for response or disease progression.

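### The primary complete response rate has two unreconciled definitions: at 1 year in the synopsis, best overall response up to progression in Section 9.6

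*Combined protocol and SAP*

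**What the plan says.** In the synopsis, the Efficacy Endpoints row states that the primary objective concerns efficacy "as defined by complete response rate at 1 year of therapy". The next sentence there promises a two-sided exact 95% interval for the complete response rate.

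Section 9.6 gives a different rule: "The CR rate is defined as the proportion of patients with a best overall response of complete response with or without marrow recovery". It also keeps patients without a response assessment in the denominator as non-responders. Section 8.3 supplies the time frame for that rule: "The best overall response is the best response recorded from the start of treatment until disease/recurrence progression".

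The synopsis objectives, the synopsis statistical paragraph, Section 2.1 and Section 9.1 all speak of a complete remission or response rate without a time point.

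On the schedule, Section 4.1 places the first response assessment before cycle 12 is complete and then adds: "Repeat response assessments will be performed at 24 cycles of therapy for those continuing on acalabrutinib". Note 6 to Table 5.1 agrees: "CT Scan/Response assessment end of cycle 12 and at the end of cycle 24 for patients continuing on acalabrutinib". Section 4.1 also keeps patients who are not in MRD-negative complete response at cycle 12 on acalabrutinib.

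**The concern.** The two definitions differ for a group of patients that the design itself allows for. A patient short of complete response at cycle 12 continues acalabrutinib, is assessed again at cycle 24, and may reach a first complete response there. That patient is a responder under Section 9.6 and a non-responder under the synopsis. Every patient in complete response at cycle 12 counts under both, so the Section 9.6 rate can only equal or exceed the 1-year rate.

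What is at stake is the trial's main result, a single proportion with its interval. The study is open-label, single-arm and single-center. If the definition is not settled beforehand, the choice between the two rates could be made once the responses are known, and any difference between them runs in one direction.

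The definitions also answer different questions. Section 1.6 proposes that the combination "will increase the efficacy of therapy for CLL by decreasing the time of achievement of complete response". A rate at about 1 year bears on that. A best response that may arise at any time before progression does not measure speed.

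**Working it through.** **Timing.** Section 4.1 sets every cycle at 28 days.
- End of cycle 12: 12 × 28 = 336 days.
- End of cycle 24: 24 × 28 = 672 days, which is 672 − 365 = 307 days past one year.
- Section 8 allows a 7-day window either side of an efficacy assessment. The earliest cycle-24 assessment is then day 672 − 7 = 665, still 665 − 365 = 300 days past one year. No reading of 1 year takes in cycle 24.

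**The plan's own precision figures.** Sections 9.1 and 9.6 supply the inputs: n = 40, an anticipated rate of 20% (x = 0.20 × 40 = 8), and a two-sided exact 95% interval. The Clopper-Pearson limits are
- lower: the 0.025 quantile of Beta(x, n − x + 1)
- upper: the 0.975 quantile of Beta(x + 1, n − x)

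For x = 8 these give 9.05% to 35.65%, width 26.6 points, as Section 9.1 states. The largest width over all x is 32.4 points, at x = 20, which also agrees. These figures do not show which definition was meant: the 20% carries no time point, and n is 40 either way.

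**Effect of late responses.** Assume that 40 patients are treated and that 8 are in complete response at cycle 12. Let k more have a first complete response at cycle 24. The documents give no value for k, so these rows are illustrations.

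| k | Synopsis rate (95% interval) | Section 9.6 rate (95% interval) |
|---|---|---|
| 0 | 8/40 = 20.0% (9.1% to 35.6%) | 8/40 = 20.0% (9.1% to 35.6%) |
| 1 | unchanged | 9/40 = 22.5% (10.8% to 38.5%) |
| 2 | unchanged | 10/40 = 25.0% (12.7% to 41.2%) |
| 4 | unchanged | 12/40 = 30.0% (16.6% to 46.5%) |

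Each late response adds 1/40 = 2.5 points. Each interval is valid for its own definition; what changes is the quantity being estimated.

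**The case against.** The best defense is that the two places can be read together. Only the synopsis gives the primary measure a time point, and Section 9.6 never calls its rate primary. One could take the time from the synopsis, and take from Section 9.6 which response categories count and how missing assessments are handled. The sections that name no time contradict neither. This has some force, and the defect is best described as an unreconciled time point. It does not remove the problem, because Section 9.6 uses the term best overall response and Section 8.3 gives that term a time frame running to progression.

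It can also be said that dated responses allow both rates to be tabulated, and that nothing in this estimation-only design is tested against a threshold. Both are true, and they limit the harm. They do not settle which rate is the headline.

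Three stronger readings are tempting, and the documents support none of them.
- A reader might infer that the plan delivers only the open-ended rate. The synopsis is part of the plan and names the 1-year rate.
- A reader might infer that 1 year is tied to no assessment, because treatment delays could push cycle 12 beyond a calendar year. Cycle 12 is the only scheduled response assessment near one year. Section 7.1 does not say that a delay shifts the cycle count, and a drift of some days would be immaterial.
- A reader might infer that best overall response has no end at all. Section 8.3 ends it at progression; what it lacks is a cycle or calendar limit.

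**Conclusion.** The point holds as a mismatch between current sections. The synopsis fixes the primary complete response rate at 1 year, Sections 9.6 and 8.3 together define it up to progression, and nothing ranks one above the other. It should be fixed, but its reach is limited to the primary estimate and its interval. The precision calculation in Section 9.1 is correct.

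The size is 2.5 points for each complete response first documented at cycle 24, assuming 40 treated patients. It is zero if there are none, and the documents offer no basis for forecasting the number.

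**What to change.** State one primary definition, in the same words, in the synopsis, Section 2.1, Section 9.1 and Section 9.6. The definition that fits the synopsis and the hypothesis of faster response is the proportion of treated patients in CR or CRi at the end-of-cycle-12 response assessment. Keep the existing Section 9.6 rule that patients without an assessment stay in the denominator as non-responders. Report the best overall complete response rate, including cycle 24, as a secondary endpoint with its own exact 95% interval. Say in Section 9.1 which of the two rates the anticipated 20% refers to.

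If best overall response is the intended primary measure, correct the synopsis instead and give it a cut-off. One is needed because Section 8 leaves efficacy assessments after cycle 24 to investigator discretion or standard of care.

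No new assessment is required, since both are already scheduled. The cost is a protocol amendment, which Section 11.1 sends to the IRB for approval, and a headline rate that may be lower than the best overall rate.

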Despite these advancements, CLL remains an incurable disease, and many patients will progress and eventually die from their disease or the complications of its therapies such as infection. Furthermore, patients with higher risk cytogenetic abnormalities still present with a less than optimal response to approved therapies and shorter duration of response and progression free survival. As such, there is a pressing need for new, innovative, targeted therapies (and novel combinations of these therapies) for the treatment of patients with relapsed/refractory CLL. Despite this progress treatment of CLL remains suboptimal. Patients do not recover immune competency resulting in complications including infections, second malignancies, and autoimmune cytopenias. Currently therapies using B cell receptor pathway inhibitors are continued until disease progression or intolerance. About 30% of patients stop therapy because of adverse events and a smaller percentage stop because of disease progression.[7] The development of a well-tolerated more effective, easily administered and limited duration therapy combining a specifically targeted BTK inhibitor and an anti-CD20 mAb would be a major contribution to the management of CLL and other B cell malignancies.

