4.3 DISCONTINUATION FROM STUDY TREATMENT

Patients will be discontinued from study treatment for any of the following reasons:

- MRD negative CR or CRI at completion of cycle 12 or cycle 24 (MRD negativity is defined as <1 CLL cell/10,000)
- Disease progression
- Severe toxicity
- Patient requests to withdraw consent or discontinue treatment
- Pregnancy

- Inability of the patient to comply with study requirements
- Conditions requiring therapeutic intervention not permitted by the protocol
- Non-compliance/lost to follow-up
- Investigator discretion
- Study termination

Patients who discontinue from study treatment (for reasons other than progressive disease) will continue to be followed for progression. After withdrawal from protocol treatment, patients should be followed for AEs for 30 calendar days after their last dose of study drug. All new AEs occurring during this period must be reported and followed until resolution, unless, in the opinion of the investigator, these values are not likely to improve because of the underlying disease. In this case the investigators must record his or her reasoning for this decision in the patient's medical records. All patients who have CTCAE Grade 3 or 4 laboratory abnormalities at the time of withdrawal should be followed until the laboratory values have returned to Grade 1 or 2, unless in the opinion of the investigator, it is not likely that these values are to improve because of the underlying disease. In this case, the investigator must record his or her reasoning for making this decision in the patient's medical records.

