5 STUDY ASSESSMENTS AND TREATMENT SCHEDULE

Table 5.1 below lists all of the required assessments that should be performed at each study visit.

TABLE 5.1: STUDY ASSESSMENTS AND TREATMENT SCHEDULE

Cycle = 28 days	Screening	Cycle 1 ¹				Cycle 2-6 ²	Cycle 7-12 ²	Cycles 12-24 ²	Follow up ³
	D-28 to -1	D1	D3,4 or 5	D8	D15	D1	D1	q3 mo	
Informed consent	X								
Medical history	X								
ECOG Performance Status	X								
Physical Examination	X	X		X		X	X	X	
Vital signs	X	X	X	X		X	X	X	
Hematology ¹⁴	X	X	X	X	X	X	X	X	
Chemistry ¹⁵	X	X ¹⁶				X	X	X	
LDH, Uric acid	X	X ¹⁶							
B2mcg	X								
Pregnancy Test	X ⁸								
Hep B/C serology, quant IgG	X								
FISH	X ⁵								
IGHV, TP53, NOTCH1, SF3B1	X ⁵								
CT imaging (neck, chest, abdomen, pelvis)	X ⁶					X ⁶	X ⁶		
BM aspirate & biopsy						X ⁹	X ⁹		
Flow cytometry for MRD						X ¹⁰	X ¹⁰		
Correlative Labs ⁴	X	X	X	X	X	X	X	X	
Rituximab 50 mg* twice weekly	X*	X	X	X	X				
Acalabrutinib 100 mg BID			X ¹³	X	X	X	X ¹²	X ¹²	
Response Assessment						X	X		
Adverse Event Assessment		X	X	X	X	X	X	X	X ¹¹
Concomitant Medications		X	X	X	X	X	X	X	

*1st dose of rituximab will be administered intravenously, subsequently doses will be administered subcutaneously

¹ Treatment Administration +/- 1 day window. Physical Exam, Vital Signs, Hematology and Chem visit days have - 1 day window

² Treatment Administration +/- 3 day window. Physical Exam, Vital Signs, Hematology and Chem visit days have a - 3 day window

³ Following completion of cycle 24 or upon discontinuation of therapy in the absence of disease progression, patients will be evaluated as per institutional standards (typically every 3-4 months). Physical exam data, vital signs, laboratory values and patient diaries will no longer be collected. Patients continuing on acalabrutinib will continue with adverse event assessments at each evaluation and be followed for progression and survival events.

⁴ See section 12

⁵ FISH for del17p, del11q, del13q, trisomy 12 will be performed on peripheral blood or marrow within 6 months of C1D1. IGHV, TP53, NOTCH1, SF3B1 mutation analysis to be performed at screening (if feasible) unless previously tested.

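### Section 9.6 tabulates adverse events by drug received in a one-arm trial, with no treatment-period split, common horizon or patient-time measure

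*Combined protocol and SAP*

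**What the plan says.** Section 9.1: "This is a single-arm, single-center prospective study". Section 4.1 has every patient start rituximab on day 1 and acalabrutinib on day 8. Rituximab ends after six 28-day cycles. Acalabrutinib stops by plan only for an MRD-negative CR at cycle 12 or cycle 24; the other patients continue it with no fixed maximum (sections 4.1 and 8).

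Section 9.6 takes everyone who received at least one dose as the safety population. "Safety evaluations will be based on the incidence, intensity, and type of adverse events", together with examination, vital-sign and laboratory changes. It adds: "Safety variables will be tabulated and presented by study drug actually received". It gives no treatment periods, no time unit and no cut-off date. Section 9.4 summarizes dose and duration but does not link them to adverse events.

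On collection, section 4.3 says that after withdrawal from treatment "patients should be followed for AEs for 30 calendar days after their last dose of study drug", and section 10.5 sets the same limit. Table 5.1 footnote 3 covers the time after cycle 24 or after stopping. Examination, vital-sign and laboratory data are then no longer collected, and "Patients continuing on acalabrutinib will continue with adverse event assessments at each evaluation and be followed for progression and survival events". The Follow up column of Table 5.1 does mark adverse event assessment, but its footnote 11 concerns only the follow-up of SAEs.

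**The concern.** The secondary objective is the safety of acalabrutinib with rituximab, and section 1.6 hopes for treatment that is shorter and less toxic. A reader will want to know which events arose while both drugs were being given, which on acalabrutinib alone, and which after stopping. Grouping by drug received separates none of these when all patients are due both drugs. At most it would set apart someone who left before day 8.

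The length of observation also depends on response. A percentage of patients with an event rises with time observed, so without a horizon or a patient-time denominator the figure partly reflects how long patients stayed on acalabrutinib and when the data were cut.

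The introduction (section 1.1) names the late harms of interest in this disease: "Patients do not recover immune competency resulting in complications including infections, second malignancies, and autoimmune cytopenias". These are the events for which collection off treatment matters most.

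**Working it through.** **The plan's own figure.** The only design calculation concerns the CR rate. The exact binomial interval for 8/40 is 9.05% to 35.65%, width 26.6%, and the maximum width is 32.4%, at 20/40. Both agree with section 9.1. The plan states no safety figure.

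**Inputs from the documents.** Cycle length 28 days; rituximab for 6 cycles; acalabrutinib from day 8; planned stop at cycle 12 or 24; collection to 30 days after the last dose; anticipated CR rate 20% of 40.

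**Inputs assumed.** All event rates below. None is in the documents.

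**Step 1: observation windows** (cycles x 28 + 30 days).
- Stop at cycle 12: 336 + 30 = 366 days.
- Stop at cycle 24: 672 + 30 = 702 days.
- Continuing: no fixed end.
- Ratio of the two fixed windows: 702/366 = 1.9.

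**Step 2: what one column pools.**

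| Period | Stop at cycle 12 | Stop at cycle 24 |
|---|---|---|
| Rituximab alone, days 1-7 | 7 days | 7 days |
| Combination, days 8-168 | 161 days | 161 days |
| Acalabrutinib alone | 168 days | 504 days |
| Off treatment | 30 days | 30 days |
| Total | 366 days | 702 days |

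The combination is 161/366 = 44% of the first window and 161/702 = 23% of the second.

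**Step 3: effect on a percentage.** With a constant rate r per patient-year, incidence = 1 - exp(-r x days/365.25).

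| Assumed r | By day 366 | By day 702 |
|---|---|---|
| 0.05 | 4.9% | 9.2% |
| 0.10 | 9.5% | 17.5% |
| 0.20 | 18.2% | 31.9% |

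In each row the hazard is identical; only the window differs. At r = 0.10 the ratio is 17.5/9.5 = 1.8.

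**Step 4: why a pooled rate alone is not enough.** Assume 40 events per 100 patient-years while rituximab is given (168 days) and 10 afterwards.
- Pooled rate, stop at cycle 12: (40 x 168 + 10 x 198)/366 = 23.8 per 100 patient-years.
- Pooled rate, stop at cycle 24: (40 x 168 + 10 x 534)/702 = 17.2.
- Incidence over the same windows rises, from 21.2% to 28.1%.

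With 20 then 10, the pooled rates are 14.6 and 12.4 and the incidences 13.6% and 21.2%. Incidence goes up while the pooled rate goes down, and neither gives the rate during rituximab. Hence the split by period as well as a patient-time measure.

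**Step 5: size of the off-treatment gap.** If 20% reach CR and all are MRD-negative, at most 0.20 x 40 = 8 patients stop by plan at cycle 12. Expected number of these with a late event in the two years after collection closes = 8 x (1 - exp(-2r)): 0.3, 0.8 and 1.5 at assumed rates of 2, 5 and 10 per 100 patient-years.

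**The case against.** The strongest reply is that this is the usual on-treatment-plus-30-days convention, applied alike to everyone, for a descriptive secondary objective with no safety hypothesis. The regimen includes continued acalabrutinib, so incidence over the whole regimen is a legitimate answer. The grouping phrase might mean the drug being taken at event onset, and section 9.4 reports exposure, which a reader could set beside the adverse event table.

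Much of this stands. The overall table should stay, and days 8-168 are not the only period that bears on the objective. But section 9.6 does not say that drug at onset is meant, and setting a duration summary beside a percentage does not yield a rate.

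Stronger readings are tempting and are not supported:
- *Windows that never close for some patients.* One rule closes every window. It has no fixed end for continuing patients only because their dosing has none.
- *Late harm after stopping is missed.* Section 10.5 asks participants to report serious, possibly related post-study events and has the investigator notify the IRB of unanticipated ones. Open SAEs are followed to resolution. A cycle-12 stopper also has 168 + 30 = 198 days of collection after rituximab ends. The gap is active collection of non-serious events and of serious events not thought related.
- *Patients who stop will be shown as safer than those who continue.* The plan makes no such comparison.
- *The results cannot be compared with the percentages in section 1.4.* Those are themselves plain percentages of patients, given without patient-time.
- *A five-fold distortion.* That needs an assumed rate and an arbitrary 36-month point set against the end of cycle 6. The ratio fixed by the design is 1.9 in window length.

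**Conclusion.** The point holds as a cheap improvement. The stated grouping separates nothing useful in this design, and adverse event incidence is left without periods, horizon, patient-time or cut-off, while planned observation differs 1.9-fold between the two planned stops and is longer still for patients who continue past cycle 24. The 1.9-fold figure needs no assumption about event rates. The incidences (9.5% against 17.5% at 0.10 per patient-year) rest on an assumed constant rate and only illustrate the effect.

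The one-column result is the natural reading of section 9.6, not a certain one. The off-treatment gap is real but narrow: at most about 8 of 40 patients would stop by plan at cycle 12 on the anticipated CR rate, so late-event counts will be small. The sample size, the CR interval and all dose, schedule and stopping rules are unaffected.

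**What to change.** In section 9.6, keep the overall incidence table and replace the grouping by drug received with:

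1. Number and percentage of patients with events by period of onset: rituximab alone; combination (first acalabrutinib dose to last rituximab dose, or to a stated lag used consistently); acalabrutinib alone; off treatment. The denominator for each is the patients under adverse event observation at the start of that period.
2. Incidence over a common horizon, through cycle 12 plus 30 days (day 366), and exposure-adjusted incidence, overall and by period, with exact confidence intervals, at a stated safety cut-off. Count patients with a first event per patient-year at risk, so that repeated events in one patient do not distort the interval.

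In addition, record second malignancies, Grade 3 or higher infections and autoimmune cytopenias for all patients, on or off therapy, at the follow-up visits already used for progression. Reconcile the Follow up column of Table 5.1 and its footnotes 3 and 11 with sections 4.3 and 10.5, so that it is clear which adverse event data are collected off treatment.

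The cost is more table rows, built from adverse event and dosing records already kept, and one CRF item at visits that already take place. Later periods will be sparse and their intervals wide.
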